Given the decreasing number of third- and fourth degree lacerations and poor resident confidence and performance demonstrated in these repairs, better and more widely used teaching methods are necessary. The modified beef tongue model serves as a realistic tool to teach and assess fourth-degree laceration anatomy and repair. While workshops have been shown to improve knowledge and technical skills [3], these require significant time, expense, and organization. Instructional videos can be used to serve the same purpose without these limitations and thus could lead to wider use as a didactic intervention for fourth-degree repair. Instructional videos have been evaluated for fourth-degree repair in a limited manner. One study showed an improvement in knowledge after an instructional video but only in residents with no prior experience in repair of lacerations [8] and we could not find any that assess change in outcomes on technical surgical skills.

We believe that an instructional video that utilizes the modified beef tongue model is a valuable educational tool to increase resident knowledge, confidence, and surgical ability to properly repair a fourth degree laceration. The aim of this study is to compare technical skills outcomes with an instructional video using the modified beef tongue model to a modified beef tongue hands-on educational workshop. Our hypothesis is that participants will have similar

improvements in their technical skills for repair of fourth-degree laceration as evaluated by an objective structured assessment of technical skills (OSATS).

Null hypothesis: Participants undergoing the modified beef tongue instructional video will have worse outcomes on an objective structured assessment of technical skills (OSATS) for repair of fourth degree obstetric laceration than those undergoing a modified beef tongue educational workshop.

Significance

There are no studies evaluating the use of an instructional video for fourth-degree laceration repair to assess change in outcomes on technical skills.

Study Design

Inclusion Criteria

PGY1-4 residents in an obstetrics and gynecology training program

Exclusion Criteria

None

Intervention

Instructional video using the modified beef tongue model or instructional workshop using the modified beef tongue model.

Primary outcome

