The primary outcome will be change in technical skills score measured as change from baseline in a validated objective structured assessment of technical skills (OSATS) for repair of fourth degree obstetric laceration.

Secondary outcomes

1. Participant preference of model between instructional video and instructional workshop
2. Knowledge assessed by written test performed pre- and post-intervention
3. Participant's confidence in fourth-degree laceration repair as measured by change in confidence score from pre- to post-intervention.
4. Time taken for repair of fourth degree laceration
5. Ease of use of the model as reported by participants
6. Overall satisfaction of the model
7. Model realism
8. Factors associated with higher knowledge scores (e.g. PGY level, number of prior repairs, prior didactics)

Protocol in detail

Institutional Review Board approval and written informed consent will be obtained prior to initiation of the study. All obstetrics and gynecology residents at the University of Alabama will be eligible for the study.

Eligible residents who desire will be enrolled and consented for the trial. Participants will then complete a short pre-intervention knowledge assessment written test and be asked to rate their confidence level in completing a fourth-degree repair based on a Likert scale. The written test is the same as the one used by Patel et al to evaluate residents' knowledge about

fourth-degree laceration repair [8]. The questions are based on Williams's obstetric chapter on episiotomy repair [11] and showed construct validity given a significant difference in scores between postgraduate year (PGY)-1 and PGY-4 residents [8]. Participants will also complete a baseline objective structured assessment of technical skills (OSATS) assessment for repair of fourth-degree obstetric laceration on a commercial anatomical replica, the Sultan Anal Sphincter Trainer (Limbs & Things Inc, Savannah, Georgia). This model comes with a replaceable perineal pad that allows approximately 24 repairs before replacement is necessary. The validated OSATS used will be the assessment described by Siddiqui et al and validated on a surgical model [9]. The repair will be videotaped and then distributed to evaluators who will use the 20 item task specific checklist described by Siddiqui et al [9]. The time taken for the repair will be recorded.

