Demographic and baseline data will be collected on the participants including PGY level, number of fourth-degree lacerations performed, whether they have read a textbook regarding fourth-degree laceration repair, whether they have read a journal article regarding fourth-degree laceration repair, whether they have attended a didactic session in pelvic anatomy, and whether they have attended a didactic session on fourth-degree laceration repair.

Participants will then be randomized into two groups. Randomization will be performed using a computer-generated block design so that each group has a balanced number of residents in each postgraduate year training level. One group will be randomized to the modified beef tongue video and one will be randomized to the modified beef tongue instructional workshop. The modified beef tongue video group will be given an instructional video created using the modified beef tongue model to show anatomy and proper repair of the laceration. The group randomized to the modified beef tongue instructional workshop will undergo an interactive

workshop using the modified beef tongue model to show anatomy and proper repair of the laceration.

The modified beef tongue for the video and workshop will be prepared according to the model previously described in the literature [11]. The modified model includes beef tripe (small intestine) used for anal mucosa and chicken leg muscles for anal sphincter muscle analogs. The tripe is tunneled through the body of the trimmed beef tongue and sutured like an ostomy to simulate the anal canal. The tongue is incised toward the tripe “anal canal.” Chicken leg muscles are tunneled from the incision out to the cut edges of the beef tongue to create anal sphincter muscle analogs.

Following the didactic intervention, participants from each group will be given the written knowledge assessment test again and the objective structured assessment of technical skills (OSATS) for repair of fourth-degree laceration on the commercial anatomical replica again. The time taken for the repair will be recorded. Residents will also be asked to evaluate model realism, ease of use, and satisfaction using a Likert scale. The residents will be asked to assess their confidence again using a Likert scale.

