The participants will then be crossed over and those who were initially randomized to the video group will then undergo the instructional workshop and the ones initially in the workshop group will be given the instructional video. Participants will then be asked to rate their overall preference between models on a scale of 1 to 10 with 1 being the video and 10 being the instructional workshop. They will also complete the written knowledge test again.

The results of this trial may help to inform to a cost- and time-efficient manner of instruction on the repair of 3rd and 4th degree lacerations. A weakness is that it is unclear whether this will translate to effectiveness at the time of an actual third- and fourth-degree repair.

Statistical Analysis Plan

Given the fixed set of residents, a post hoc power analysis will be performed. Categorical variables will be analyzed using chi-squared or Fisher exact tests and continuous variables will be analyzed using student t-tests. The mean scores of knowledge assessment and from the Objective Structured Assessment of Technical Skills (OSATS) as well as the change in scores pre- and post-intervention will be compared using Student t-tests. Differences in improvement scores between the two groups will be further examined using linear regression models, adjusting for baseline score and year of training. Differences in the score improvement between the two study groups and for each resident year will be analyzed using Wilcoxon rank test.

References

1. Vale de Castro Monteiro M, Pereira GM, Aguiar RA, Azevedo RL, Correia-Junior MD, Reis ZS. Risk factors for severe obstetric perineal lacerations. *Int Urogynecol J* 2016;27:61–7.

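### Change in OSATS, the primary outcome, gets up to three competing between-group tests and none is named primary; the baseline- and PGY-adjusted regression already planned should be

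*Combined protocol and SAP*

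**What the plan says.** The Primary outcome section fixes the endpoint: "The primary outcome will be change in technical skills score measured as change from baseline" in a validated OSATS for fourth-degree repair. The Statistical Analysis Plan then sets out three treatments of change.

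- **t-test.** The knowledge and OSATS means are listed, "as well as the change in scores pre- and post-intervention will be compared using Student t-tests".
- **Regression.** "Differences in improvement scores between the two groups will be further examined using linear regression models, adjusting for baseline score and year of training".
- **Wilcoxon.** "Differences in the score improvement between the two study groups and for each resident year will be analyzed using Wilcoxon rank test". This sentence does not name the score. On the natural reading it includes an overall between-group test of OSATS change as well as tests within each year.

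Three other statements bear on the choice. On allocation, Protocol in detail says: "Randomization will be performed using a computer-generated block design so that each group has a balanced number of residents in each postgraduate year". On size, the Statistical Analysis Plan says: "Given the fixed set of residents, a post hoc power analysis will be performed". On the aim, the text just before the null hypothesis says: "Our hypothesis is that participants will have similar" improvements in technical skills.

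**The concern.** One endpoint has several analyses, with no order among them and no rule for disagreement. They can give different answers, and the reader of the results could not tell which had been meant to count.

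The choice also affects precision. The change-score t-test uses the baseline only by subtracting it, and does not use training year at all, although allocation is balanced on year. The number of residents is fixed, so precision lost through the analysis cannot be recovered by recruiting more. Because the trial expects similar improvement in the two groups, the width of the interval for the difference largely decides what it can conclude.

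The background also cites a study that found "an improvement in knowledge after an instructional video but only in residents with no prior experience in repair of lacerations". That concerns knowledge and prior experience, not OSATS and training year. It still makes gains that vary with seniority plausible, and in that case the unadjusted test loses more.

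**Working it through.** **Inputs.** The documents give no sample size, alpha, SD, pre-post correlation, training-year effect or margin, so there is no stated figure to reproduce. Everything below is assumed:
- four training years with 3, 4 or 5 residents per arm per year (12, 16 or 20 per arm)
- normal scores, in units of the post-score SD
- two-sided alpha of 0.05
- pre-post correlation r, and q = baseline SD / post SD

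**Large-sample comparison.** The variance of the change-score difference relative to the baseline-adjusted difference is (1 + q² − 2rq)/(1 − r²). Numerator minus denominator is (q − r)². The ratio is therefore never below 1, and equals 1 only when q = r.
- q = 1: 1.40/0.91 = 1.54 at r = 0.3; 1.00/0.75 = 1.33 at r = 0.5; 0.60/0.51 = 1.18 at r = 0.7; 0.20/0.19 = 1.05 at r = 0.9.
- q = 0.7: 1.07/0.91 = 1.18 at r = 0.3; 0.79/0.75 = 1.05 at r = 0.5; 0.51/0.51 = 1.00 at r = 0.7.

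**Small-sample cost.** With 32 residents the t-test has 30 degrees of freedom. The regression (intercept, group, baseline, three year terms) has 32 − 6 = 26. For q = 1 and r = 0.5, the expected half-widths are about:
- t-test: 2.042 × √(2(1 − 0.5)) × √(2/16) = 0.72
- regression: 2.056 × √(1 − 0.25) × √(2/16) = 0.63, and slightly more once chance baseline imbalance is counted

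**Simulation, 16 per arm, q = 1** (8,000 replicates per setting). Each cell is t-test v regression.

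| r | Mean 95% CI half-width (SD) | Power at 0.8 SD | Same, if gains differ by year |
|---|---|---|---|
| 0.3 | 0.85 v 0.70 | 45 v 60% | 38 v 60% |
| 0.5 | 0.72 v 0.64 | 59 v 68% | 49 v 69% |
| 0.7 | 0.56 v 0.52 | 80 v 84% | 69 v 85% |

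The last column adds a linear year trend of SD 0.7 at baseline and SD 0.5 in the gain (5,000 replicates).

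Half-widths at r = 0.3, 0.5 and 0.7 for the other sizes:
- 12 per arm: 0.99 v 0.83, 0.84 v 0.75, 0.65 v 0.62
- 20 per arm: 0.75 v 0.62, 0.64 v 0.56, 0.49 v 0.46

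**Where the gain disappears.**
- r = 0.9: 0.32 v 0.32 at 16 per arm; 0.374 v 0.379 at 12 per arm
- q = 0.7, 16 per arm: 0.64 v 0.64 at r = 0.5; 0.51 v 0.52 at r = 0.7

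**Disagreement on significance** (16 per arm, q = 1, r = 0.3, 0.5, 0.7).
- True difference 0.8 SD: t-test and regression disagree in about 24%, 18% and 10% of trials; all three tests fail to agree in about 29%, 23% and 14%.
- No true difference: t-test and regression disagree in about 6%, 5% and 3%.

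**Type I error.** If any of the three tests may be claimed, at least one rejects with no true difference in about 8% of trials (7–9% over 12–20 per arm and r = 0.3–0.7). The tests are strongly correlated, so this stays well below the 1 − 0.95³ = 14% for independent tests. The regression alone rejects in about 5%.

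**The case against.** The strongest reply is that an order can be inferred. The t-test comes first and the regression is introduced as a further examination, so the t-test could be read as primary and the regression as supportive. That reading is fair, but it is an inference and not a designation, and a third test follows. If it is correct, the primary test is the one that ignores baseline and training year, which strengthens the case for changing it.

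Naming the t-test primary would also cure the ambiguity. It is a valid test under randomization and matches the endpoint as worded. This stands: preferring the regression is a judgement about precision. The regression is, however, equally faithful to the endpoint. With baseline in the model, the estimated group difference is the same whether the response is change or post-training score.

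The power and disagreement figures at 0.8 SD are two-sided superiority figures, while the trial expects similarity and its null is that video is worse. This also stands; CI half-width is the measure that fits the aim. The ambiguity does not vanish under the other framing. With an invented non-inferiority margin of 0.8 SD and no true difference, the t-test and regression disagree in about 23%, 18% and 10% of trials at r = 0.3, 0.5 and 0.7. The documents give no margin, so this is illustration only.

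Finally, the Wilcoxon sentence may mean only comparisons within each year. The three-test figures then fall away, but the t-test and the regression remain unranked.

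**Conclusion.** The concern holds. The plan names no primary analysis for its primary outcome, and at least two planned analyses compete for it. Under equal SDs and 16 per arm, adjustment shortens the interval by 0.15, 0.08 and 0.04 SD at r = 0.3, 0.5 and 0.7. Against that, the worst loss among the cases examined is about 0.01 SD. The rise in type I error from choosing among the tests is modest. The larger risk is that the most favourable estimate and interval could be selected once the data are seen.

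The missing designation is a matter of text and is certain. The size of the precision gain is less certain, because sample size, SDs, correlation and training-year effects are all assumed. The differing-gains case in particular rests on indirect evidence. The change is worth making, but the point does not invalidate the trial.

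**What to change.** State in the Statistical Analysis Plan that the single primary analysis is the linear model already planned: change in OSATS on randomized group, baseline OSATS and PGY year (three indicator terms). Report the adjusted group difference with its 95% CI. Label the unadjusted t-tests and the overall Wilcoxon test as sensitivity analyses, and say explicitly whether the Wilcoxon sentence covers OSATS change. Present results by training year as exploratory estimates with CIs.

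The cost is wording. Baseline OSATS and PGY level are already to be collected. The model spends four degrees of freedom (one for baseline, three for year), which the simulated figures include and which account for the very small loss in the unfavourable cases. The change does not supply a non-inferiority margin, which the stated null hypothesis needs and which must be settled separately; the adjusted difference and its CI would be the quantity to set against that margin.
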